#### *UTI definitions*

There is debate over the optimal definition for recurrent UTI. In general, the most commonly accepted definition is the presence of 3 or more symptomatic UTI in 1 year or 2 in 6 months [16]. Symptomatic UTI has been defined by the Center for Disease Control (CDC) as a combination of signs, symptoms and laboratory measures. We will use this definition of UTI for our primary outcome: individuals experiencing at least one symptom (fever >38 degrees C, urgency, frequency, dysuria OR suprapubic tenderness) AND a positive urine culture that is  $\geq 10^5$  microorganisms per milliliter (mL) of urine with no more than 2 species of microorganisms. Alternatively, if the specimen is collected via catheterization, a culture as low as  $10^3$  microorganisms per mL of urine will be considered positive. Given that guidelines do not require primary care physicians to obtain urine cultures to diagnose a urinary tract infection, we will only require one positive urine culture and the other urinary tract infections may be diagnosed with urinalysis. From a practical and clinical standpoint, UTIs are generally diagnosed based on symptoms, urine analysis and/or culture and rarely are catheterized specimens collected in routine practice. Thus, presence of UTI will be determined using symptoms and a positive clean-catch culture as the primary outcome unless a patient cannot obtain a clean catch (in which case we will use a catheterized specimen). In order to minimize false positives, urine will be placed in preservative within 10 min of collection. Urine cultures are up to 95% sensitive and 99% specific at diagnosing UTI [17].

#### **• Innovation**

Given the high prevalence of recurrent UTI in the postmenopausal population, the growing elderly population and the increasing prevalence of multidrug resistant bacterial infections, prevention of UTI in this high-risk population is of utmost importance. Recurrent UTI does not currently have one accepted treatment and various regimens are used based on provider preference. One option is the use of cranberry, although a recent Cochrane review shows a smaller benefit than previously thought with cranberry performing similarly to placebo, water and no treatment (RR0.86, 95% CI 0.71 to 1.04) [18]. Other options include antibiotic suppression with daily treatment. Nitrofurantoin, cephalexin and trimethoprim/sulfamethoxazole have all been proven effective at preventing recurrent UTI when taken daily for prophylaxis with success rates ranging from 36-94% [19-22]. Patients who associate their UTIs with sexual intercourse have had 66-68% success with postcoital treatment with single dosing of antibiotic [23-25]. However, treating prophylactically with antibiotics has undesirable side effects such as promoting fungal infections, gastro intestinal flora upset, and resistance, making recurrent infections harder to treat. In addition, these antibiotics can have serious side effects including blood dyscrasias, pulmonary fibrosis, tendon rupture, peripheral neuropathy, hepato and renal toxicity.

Prevention of recurrent urinary tract infection could greatly minimize the problems associated with chronic administration of antibiotics. While use of vaginal estrogen is often routine practice for prevention of UTI, only one study has ever explored using vaginal estrogen for this purpose in a randomized controlled trial and this study used a higher dose than currently used in clinical practice [15]. As such, there is no data on the efficacy of vaginal estrogen using modern doses and formulations. We hope that these results will help us better understand treatment for a disease where there is no ‘gold standard’. Using evidence from a randomized placebo controlled trial will allow us to definitively report on the efficacy of vaginal estrogen in the prevention of recurrent UTI and explore satisfaction, quality of life and efficacy between two commonly used preparations.

## 8. PROGRESS REPORT

We have completed enrollment.

## 9. RESEARCH DESIGN AND METHODS

[figure not shown]
### **Overall Design**

This is an investigator initiated, multicenter, single blind, randomized placebo controlled trial of vaginal estrogen (delivered by ring or cream) compared to placebo control. During the blinded portion, subjects will be randomized to either receive vaginal estrogen (via ring or cream), or receive a placebo cream. Conjugated estrogen cream at a strength of 0.625mg/g and a dose of 0.5g (0.312 mg) twice a week will be used, as will estradiol ring containing 2mg of estradiol placed vaginally every 3 months. These two doses are standard clinical dosing based on FDA approved treatment of vaginal atrophy and result in similar vaginal effects. The placebo cream will be a commercially available over the counter oil based vaginal lubricant which is semi-solid at room temperature and contains no active ingredients. Primary outcome will be assessed at 6 months with vaginal estrogen group compared to the placebo control. However, in order to improve recruitment and assess long term compliance, satisfaction and efficacy in the as treated groups, we will offer open label use of ring or active cream after 6 months of blinded treatment. Those on placebo at 6 months will be allowed to choose which vaginal estrogen form (ring or cream) she would like to use for another 6 months and secondary outcomes captured after their 6 months of active treatment will be combined with those 6 month measures collected from those originally randomized to active therapy. Vaginal estrogen group will also be allowed to choose which administration (ring or cream) they would like to continue with at 6 months. Subjects will not be told which preparation is the placebo in order for them to remain blinded to treatment. Providers, however, will not be blind to this. We chose not to use a placebo ring, as we felt this could be a nidus for infection skewing the results and unnecessarily placing subjects at risk. We will attempt to minimize bias by having providers blinded to outcome measures and questionnaire responses.

The primary outcome is occurrence of one or more symptomatic UTIs within 6 months of treatment. Subjects will perform a clean catch for a urine culture when they have symptoms of a UTI using the CDC definition of symptoms, as above. If the subject cannot perform a clean catch themselves, a provider may obtain a catheterized specimen as clinically indicated, in which case the threshold for bacterial count will decrease to  $10^3$  microorganisms per mL. Secondary outcomes include assessing rate of UTI over the course of the year in those women who received placebo and then vaginal estrogen, as well as comparing the rates of UTI in the placebo and vaginal estrogen group. Quality of life (QOL) questionnaires will be administered at baseline, at the end of randomization and at drop out or 12 months. There are no validated questionnaires that assess UTI specifically, therefore we have chosen questionnaires which relate to general QOL, as well as those which include symptoms similar to that of UTI. In addition, we know that vaginal estrogen can treat dyspareunia, so we will capture sexual function. We will be using the SF 12, as well as the overactive bladder satisfaction questionnaire (OAB-SAT-q), the medical, epidemiological and social aspects of aging questionnaire (MESA), the urogenital distress inventory (UDI-6) and the female sexual function index (FSFI) along with the patient satisfaction global ratings: patient satisfaction question (PSQ), estimated percent improvement (EPI) and global perception of improvement (GPI). The SF 12 is a general quality of life questionnaire initially used to survey health status [26]. The OAB-SAT-q is a questionnaire evaluating satisfaction pertaining to overactive bladder symptom treatment, symptoms which are similar to those of a UTI [27]. The MESA questionnaire explores lower urinary tract symptoms [28]. The UDI-6 is the short form of the urogenital distress inventory which surveys life impact and symptom distress of urinary incontinence and related issues in women [29]. The FSFI is a validated questionnaire assessing female sexual function [30]. The PSQ, EPI and GPI are patient global ratings, satisfaction, perception of improvement and estimated percent improvement validated previously in the treatment of urinary incontinence [31]. These questionnaires will allow us to assess whether general quality of life, irritative urinary symptoms, as well as sexual function are improved by vaginal estrogen, which could occur secondary to the correction of atrophic vaginitis alone. We will also assess whether QOL changes when UTIs occur with less frequency and will assess overall patient satisfaction with treatment. We will also be evaluating adherence in each treatment arm. Adherence with creams will be assessed by medication diary and weighing the tubes at each 3 month visit and vaginal rings will be accounted for by confirming that the ring is still in place in the vagina and then exchanging it for the new ring. Adherence is defined as  $\geq 80\%$  usage.

The open label portion of the study will start at month 6. All of those women using placebo cream will be allowed to choose a vaginal estrogen preparation to use for the remainder of the study (ring or cream). Those women initially randomized to vaginal estrogen will be allowed to choose which vaginal estrogen preparation they want to continue with. The rationale behind an open label portion of the study is an incentive to participate. Vaginal estrogen is available to patients via prescription, as an off label indication, but coverage for this therapy can be limited and treatment costly (up to \$300 per prescription refill). The open label portion of the study should provide incentive for women to enroll when the study drug is already available, as will modest reimbursement for study visits. We will also be able to compare the rates of UTI in those women who received placebo initially to their rate of UTI on drug.

Eligible women will be consented and block randomized using preset, opaque and sealed envelopes. These cards will either say “study drug 1, 2 or 3” and will be placed in numbered envelopes in a random order and selected by study staff and dispensed to the subject. These drugs will be stored in a locked cabinet in the Female Pelvic Medicine clinic. After the subject receives her study drug, she will receive administration instructions. If the assigned treatment is a ring, the subject will have it placed by the provider, if it is a cream, the cream will be weighed at baseline and she will be shown how to place it vaginally herself and instructed on bringing the remaining study drug to each 3 month visit for weighing.

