### ***Safety and Toxicity Measures***

If subjects in any arm develop 3 UTIs in the 6 month treatment period, they will be unblinded. If on placebo, they will be provided active study drug as would have been done at the 6 month visit or if they are on study drug, they will be treated according to the provider's clinical practice and their outcomes recorded for the remainder of the study. Six month outcome assessments will be administered early to capture QOL data for the secondary analyses. We will also be monitoring for adverse events monthly with phone calls for the first 3 months, specifically querying symptoms of pain, bleeding or abnormal discharge which would prompt evaluation for relatedness to study participation. Events related to participation will not be billed to insurance, however, any events which are part of routine clinical care (ie. UTI or other pelvic floor disorder treatment such as urinary incontinence) will be billed according to standard clinical care. After that subjects will be encouraged to call with any adverse reactions. Attribution of these events to study participation will be assigned by the investigator and reported to the IRB according to local policy.

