## **15. RISK MANAGEMENT PROCEDURES AND ADEQUACY OF RESOURCES**

### *Monitoring Plans for Safety*

Data safety and monitoring for adverse events will be overseen by a committee composed of the PI, the study statistician and research mentor. The study staff will conduct monthly telephone interviews with the subjects during the first 3 months of the study to ascertain any adverse events in the treatment arms. The subjects will then be encouraged to call should they experience any adverse reactions. The PI will be notified of any adverse events, which will be reviewed on a case-by-case basis. Any serious adverse events requiring hospitalization and/or surgical intervention will be reported to the institutional IRB within 24 hours of identification of the event. Data will be reviewed on a quarterly basis to assess for completeness, accuracy, or any trends that may require alteration of study protocol, including number of UTIs in each subject. Any errors, omissions or adverse events will be brought to the attention of the PI.

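### Keeping unblinded providers blind to outcomes cannot hold for the primary UTI outcome, and no arm-masked endpoint decision is specified

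*Combined protocol and SAP*

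**What the plan says.** Section 9, Overall Design, describes the trial as follows: "This is an investigator initiated, multicenter, single blind, randomized placebo controlled trial of vaginal estrogen". Subjects are not told which preparation is placebo. Of knowledge of treatment the plan says: "Providers, however, will not be blind to this". The safeguard offered for this is: "We will attempt to minimize bias by having providers blinded to outcome measures and questionnaire responses".

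The same section defines the primary endpoint: "The primary outcome is occurrence of one or more symptomatic UTIs within 6 months of treatment". Under UTI definitions (section 7), an episode needs at least one listed symptom plus a positive culture. The threshold is 10^5 organisms per mL for a clean catch and 10^3 for a catheter specimen.

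Four other places describe how UTIs are handled:
- **Overall Design**, for women who cannot give a clean catch: "a provider may obtain a catheterized specimen as clinically indicated".
- **Outcomes (section 9)**: cultures run through standing laboratory orders when a subject reports symptoms. Treatment is left to the treating physician, whose recommendation also governs catheter collection.
- **Safety and Toxicity Measures (section 9)**, repeated in Potential Risks (section 14): "If subjects in any arm develop 3 UTIs in the 6 month treatment period, they will be unblinded". What follows depends on the arm.
- **Monitoring Plans for Safety (section 15)**: the quarterly data review looks for "any trends that may require alteration of study protocol, including number of UTIs in each subject".

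**The concern.** Where clinicians know the arm, the usual protection is that someone masked to arm decides whether the endpoint occurred. This plan relies instead on clinicians not seeing outcomes. The primary outcome, however, is a clinical event that those clinicians treat, so for that endpoint the protection cannot operate as written.

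A reader of the protocol, or of a paper that repeats the sentence, would credit the primary comparison with a safeguard it does not have. At stake is the classification of episodes in a trial planned around 40 women completing 6 months. If knowledge of the arm affects which episodes are sampled by catheter or counted, the error is differential: it shifts the treatment comparison instead of merely adding noise.

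**Working it through.** **Step 1. Is the safeguard compatible with the procedures?**

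| Procedure | Must someone who knows the arm learn of the UTI? |
|---|---|
| Treatment at the treating physician's discretion (Outcomes) | Yes, to treat it |
| Catheter specimen by a provider (Overall Design, Outcomes) | Yes, the suspected episode is known when the specimen is taken |
| Action by arm at the third UTI (Safety and Toxicity Measures, Potential Risks) | Yes, both count and arm are needed |
| Quarterly review of UTIs per subject (Monitoring Plans for Safety) | Not established; that sentence names no reviewer |
| Questionnaire responses | No; nothing shows providers seeing them |

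The first three rows contradict outcome blinding for UTIs. The fourth is not needed for the conclusion. No section names a masked assessor or says who makes the final call on an episode.

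**Step 2. Threshold ratio.** 10^5 / 10^3 = 100. A catheter specimen counts as positive at a concentration 100 times lower.

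**Step 3. Reproduce the plan's power.** Inputs from Sample Size Consideration: 63% placebo, 16% active, 20 per group, Fisher's exact test, two-sided 0.05. Power is the sum, over all pairs (x, y) with Fisher p ≤ 0.05, of Bin(x; 20, 0.63) × Bin(y; 20, 0.16). The result is 82.3%, consistent with the stated 80%.

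**Step 4. Effect of differential recording (assumed sizes).** Use the same sum with no true effect: placebo recorded at 63%, estrogen recorded at 63% minus d.

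| d (points) | Estrogen recorded | Fisher rejection rate |
|---|---|---|
| 0 | 63% | 2.5% |
| 5 | 58% | 3.1% |
| 10 | 53% | 5.2% |
| 15 | 48% | 8.8% |
| 20 | 43% | 14.5% |

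Fisher's test starts well below its nominal 5%. A one-arm gap of about 10 points uses up that margin; larger gaps exceed it.

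**Step 5. Sensitivity of a single result.** The planned rates give 0.63 × 20 = 12.6 and 0.16 × 20 = 3.2, so about 13/20 v 3/20, p = 0.003. Moving one woman in each arm toward the null (12/20 v 4/20) gives p = 0.022, still significant. A smaller observed difference is more fragile: 10/20 v 4/20 gives p = 0.096, and moving one woman in each arm the other way (11/20 v 3/20) gives p = 0.019.

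**The case against.** The plan discloses single blinding, gives a reason (a placebo ring might itself promote infection) and promises only an attempt. Symptoms are reported by women who are not told which preparation is placebo, culture is a laboratory result, and the rule is numerical. This leaves less room for bias than a clinician-rated endpoint would, and that argument stands.

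Several stronger readings are tempting, but the documents do not support them:
- **That the protection is absent altogether.** The sentence also covers questionnaire responses, and nothing contradicts that part.
- **That providers can choose the lower threshold.** Catheter use is limited to women who cannot give a clean catch, and UTI definitions says such specimens are rare in routine practice. Some discretion remains, because the plan requires no record or check of the inability.
- **That unblinded providers decide whether an episode counts.** The plan does not say who decides. The gap is silence.
- **That treating providers or the principal investigator review UTI counts each quarter.** The safety committee comprises the principal investigator, the study statistician and a research mentor, but the review sentence names no one. That the principal investigator also treats subjects is an inference.
- **That two reclassified women would change the conclusion.** This is true of a table chosen near the boundary, such as 10/20 v 4/20. It is not true of one near the planned rates.

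The word *attempt* does not rescue the sentence for UTIs, since the procedures themselves require providers to learn of them.

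**Conclusion.** The concern holds for the primary outcome only. The stated outcome blinding of providers is incompatible with their role in managing suspected UTIs, collecting catheter specimens and acting on the three-UTI rule, and no arm-masked derivation of the endpoint is specified.

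The size of any bias is unknown. The documents give neither a misclassification rate nor the frequency of catheter specimens. The rejection rates in the working assume no true effect, a 63% placebo rate, 20 women per group and error in one arm only. They illustrate sensitivity and do not estimate what happened. On those assumptions a 5-point gap matters little, a 10-point gap takes the test to about its nominal level, and a 20-point gap nearly triples that level. This is worth correcting because it touches the primary endpoint and the remedy is cheap.

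**What to change.** 1. Limit the Overall Design sentence to questionnaire responses, and state that treating providers will know of UTIs.
2. Name a staff statistician who does not see arm-level monitoring data. That person applies the UTI definitions rule to symptom records and culture reports with arm codes removed, and locks the result before allocation is merged. Two points need care: the study statistician sits on the safety committee, and the data that section 16 promises statisticians are de-identified, which does not mean arm-masked.
3. Add a sensitivity analysis that applies 10^5 per mL to every specimen. Report specimen type by arm. The first needs the numerical colony count for catheter specimens.
4. Leave the per-subject UTI review unchanged. The three-UTI rule and the quarterly review both need individual counts, so showing only counts pooled over arms would conflict with them.

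The cost is wording plus a modest share of the 100 staff-statistician hours already budgeted in section 15. The Progress Report says enrollment is complete, but these steps work on records and can still be taken if the data have not been analyzed by arm. The limit is that masked derivation protects the classification of recorded episodes. It does not remove bias that arose earlier, in symptom elicitation or specimen collection.

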**5. LAY LANGUAGE SUMMARY OR SYNOPSIS (no more than one paragraph)**

We would like to know if the use of vaginally applied estrogen can prevent the problem of repeated urinary tract infections (UTI) in women who have gone through menopause. We will use two forms of vaginal estrogen that are available by prescription (a ring and a cream) and compare their efficacy to that of a commercially available cream without any active ingredient. We are going to look at if the vaginal estrogen can prevent UTIs altogether and also the number of UTIs each group experiences over a 6 month period. After 6 months, all subjects will receive vaginal estrogen and the women will be able to choose which form of vaginal estrogen (ring or cream) they would like to use. We will then be able to compare the number of UTIs on and off active vaginal estrogen treatment within those subjects who started on the cream without estrogen. We are also going to look at quality of life before and during treatment using questionnaires and whether subjects stop using the treatments or do not use them as directed (compliance). Additionally, urine and vaginal swab specimens will be collected and processed for bacterial 16s rRNA characterization at baseline and after treatment.

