**6. SPECIFIC AIMS**

*Primary Objective*

The primary purpose of this study is to assess the efficacy of vaginal estrogen versus placebo at 6 months on the prevention of urinary tract infections (UTI) in postmenopausal women with history of recurrent UTI.

*Secondary Objectives*

- [1] a] To assess overall rates of UTI over 6 months in postmenopausal women with history of recurrent UTI receiving vaginal estrogen (ring or cream).
- b] To compare rates of UTI between 6 and 12 months of those subjects initially randomized to placebo.
- [2] To assess the impact of treatment of recurrent UTI with vaginal estrogen on quality of life at 6 and 12 months in postmenopausal women with history of recurrent UTI.
- [3] To assess compliance with vaginal estrogen (ring or cream) treatment at 12 months in postmenopausal women with history of recurrent UTI.
- [4] To assess efficacy of vaginal estrogen at 12 months in those compliant with treatment.

*Primary Hypothesis*

Vaginal estrogen (ring and cream) will be superior to placebo in the prevention of UTI at 6 months of treatment in postmenopausal women with a history of recurrent UTI.

*Secondary Hypotheses*

- [1] a] Overall rates of UTI in the first 6 month period in those women receiving vaginal estrogen will be

lower compared to those receiving placebo.

b) Rates of UTI will decrease between 6 and 12 months for those initially on placebo and subsequently using estrogen.

[2] Vaginal estrogen will result in improved QOL in postmenopausal women with history of recurrent UTI.

a) compared to placebo at 6 months.

b) compared to baseline at 12 months.

[3] Adherence with vaginal ring will be superior to cream.

[4] At 6 and 12 months, vaginal estrogen will be effective at preventing UTI in those adherent to therapy.

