**Methodology**  
*Details of the Intervention*

Women will be randomized to one of the two vaginal estrogen arms or placebo in a 1:1:2 fashion. For those randomized to the ring, the ring will be placed by the provider in 3 month intervals at their visits. Subjects randomized to cream arm will receive 0.5g (0.312 mg) conjugated estrogen vaginal cream per vagina at bedtime two times per week. The placebo cream will be administered in a similar fashion. These cream tubes will be weighed at baseline and again at the every 3 month office visits to assess adherence. They will also be given diaries to keep track of their medication administration. Subjects will be called once a month for the first 3 months by study personnel to assess for adverse events as well as UTI symptoms. After the first 3 months, a relationship will be established with study personnel and the participants will be encouraged to call with symptoms.

Written quality of life questionnaires will be administered at baseline, at the end of randomization or 6 months and at drop out (if possible) or 12 months. The questionnaires include the OAB-SAT-q, MESA, UDI-6, FSFI and PSQ, GPI and EPI rating scales and are previously validated questionnaires referenced above in *Overall Design* [26-31]. These will assess global QOL, as well as irritative bladder symptoms and sexual function. We will also collect baseline data with respect to medical history and concomitant pelvic medicine diagnoses.

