### ***Outcomes***

The primary outcome will be the occurrence of symptomatic UTI within the 6 month treatment period. Clean catch urine culture will be collected whenever subjects report symptoms of a UTI: fever (>38 degrees C), urgency, frequency, dysuria or suprapubic tenderness. Standing orders for urine analysis and culture will be present at the local institution's lab and women will be asked to have all urine labs done at the parent site as per standard clinical practice. If subjects are not able to submit a specimen to the local site, lab orders will be faxed to a local laboratory for collection and results sent to parent institution as per clinical care standards. Treatment will be up to the discretion of the treating physician. If they are unable to perform a clean catch, they may come in to the office for a catheterized specimen according to the treating physician's clinical recommendations. As these cultures would be obtained regardless of study participation, they will be obtained and billed according to standard of care. The presence of a UTI in the 6 month window will be the primary outcome of the study, but secondarily we will assess the rate of UTIs over the course of the year that occur in order to assess efficacy.

Other secondary outcomes include QOL questionnaires mentioned above. These will help us to look at changes in general QOL, as well as irritative bladder symptoms and sexual function, impacted by study drug. Adherence will also be assessed. We will weigh tubes of cream to determine adherence with creams, as well as collect medication diaries (adherence will be defined as  $\geq 80\%$  use as measured by weight of the vaginal cream tubes). For the ring, compliance will be assessed based on presence of the ring vaginally at 3 month visits.

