#### *Inclusion Criteria*

1. Postmenopausal status as defined by amenorrhea for  $\geq 12$  months, OR history of bilateral salpingoophorectomy, OR if the patient has had a hysterectomy defined by menopausal symptoms for  $>1$  year OR age  $>55$
2. Recurrent UTIs (3 or more in the last year or 2 or more in the last 6 months). Patients must have one culture documented UTI, but the others may be documented by urinalysis.
3. Ability to provide informed consent

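### The off-versus-on-estrogen UTI comparison in placebo starters has one fixed order, no time control and fewer symptom calls on estrogen, so it should be descriptive and set beside the change in estrogen starters

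*Combined protocol and SAP*

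**What the plan says.** The comparison appears in several places. The lay summary (section 5) says the trial will "compare the number of UTIs on and off active vaginal estrogen treatment within those subjects who started on the cream without estrogen", and Overall Design repeats it: "We will also be able to compare the rates of UTI in those women who received placebo initially to their rate of UTI on drug". Hypothesis 1b in section 6 gives the expected direction and names no comparator: "Rates of UTI will decrease between 6 and 12 months for those initially on placebo and subsequently using estrogen". Read alone, that sentence could mean a trend inside months 6-12; the other two places show that months 0-6 are to be set against months 6-12.

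- **Order.** "The open label portion of the study will start at month 6", and every placebo starter then takes estrogen. Under Safety and Toxicity Measures, a woman on placebo who reaches three UTIs within the 6 months is unblinded and moved to active drug at that point.
- **Detection.** Details of the Intervention: "Subjects will be called once a month for the first 3 months by study personnel to assess for adverse events as well as UTI symptoms". From then on, participants are asked to ring in. Section 15 ties the calls to the start of the study, not to the start of estrogen. Office visits continue every 3 months, and the Outcomes section provides standing urine orders and the return of outside laboratory results.
- **Analysis.** Data Analysis gives a Poisson model comparing counts between groups in each period. It specifies no within-woman model, period effect or handling of early switching for hypothesis 1b.
- **The other arm.** "Those women initially randomized to vaginal estrogen will be allowed to choose which vaginal estrogen preparation they want to continue with".

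**The concern.** In a single-sequence before-after comparison, anything that changes between the two periods is counted as drug effect. Here one such change is written into the protocol: active symptom enquiry covers half of the placebo phase and, for a woman who switches on schedule, none of the estrogen phase. If fewer UTIs come to light without calls, the estrogen phase looks better, which is the direction that hypothesis 1b predicts. Any general decline over the year would add to this. The early-switch rule may do so as well, because it ends a placebo phase at an event.

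At stake is the reading of one secondary hypothesis. A fall after month 6 could be reported as supporting efficacy when part of it reflects time and detection. Women randomized to estrogen follow the same calendar and call schedule, so the trial holds a concurrent reference that the plan does not use for this purpose.

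**Working it through.** **The plan's own figure.** There is none for hypothesis 1b. The only sizing is for the primary endpoint (63% against 16%, Fisher's exact test, two-sided 0.05, 20 evaluable per group, 80% power). Exact enumeration gives 82.3% power at 20 per group, so that figure is reproduced.

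**1. Loss of calls alone.** Assume a constant true rate and no drug effect. Let q be the share of UTIs captured in an uncalled month relative to a called one. Placebo months 4-6 are also uncalled, so the imbalance is three called months against none:

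on/off ratio = 6q / (3 + 3q) = 2q / (1 + q)

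| q | 2q / (1 + q) | ratio |
|---|---|---|
| 0.9 | 1.8 / 1.9 | 0.95 |
| 0.8 | 1.6 / 1.8 | 0.89 |
| 0.7 | 1.4 / 1.7 | 0.82 |
| 0.6 | 1.2 / 1.6 | 0.75 |

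The documents give no value for q.

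**2. False positives from loss of calls alone.** Simulation: 20 placebo starters, no drug effect, rates gamma-distributed between women (shape 1), conditional binomial test at two-sided 5%.

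| q | mean 1.0 UTI per 6 months | mean 1.7 |
|---|---|---|
| 0.8 | 4.4% | 6.1% |
| 0.7 | 5.7% | 8.8% |

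That is about 4-9%; a repeat gave about 4-8%. A second model applied the entry rule and was calibrated to about 63% of women with at least one UTI. With stable individual risk, a Poisson test declared a fall in 2.3% of trials at full capture, 4.4% at q = 0.8 and 11.8% at q = 0.6 (nominal 2.5%).

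**3. Change in risk after entry.** In the second model, selection on recent UTIs gives an on/off ratio of 1.00 if each woman's risk is stable. If risk waxes and wanes (assumed half-life 2-6 months), the ratio is 0.85-0.88 at full capture and 0.77-0.63 at q = 0.8 to 0.6.

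**4. Early switch.** A 63% risk of at least one UTI implies, if counts are Poisson, a mean of -ln(1 - 0.63) = 0.994 per 6 months. Then P(3 or more) = 7.9%, or 24 x 0.079 = 1.9 of 24 placebo women; with the gamma-distributed rates of step 2 it is 12-25%. Splitting time at the actual switch gives a within-woman ratio of about 0.90-0.92 with no drug effect, because the third UTI triggers the switch. Splitting by calendar month avoids that, but counts some on-estrogen time as off (about 5-10% of placebo-arm off time with those rates), which dilutes a true effect.

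**5. Estrogen starters as time reference.** If q is the same in both arms, the factor 2q / (1 + q) enters both arms' change and cancels. In the second model the controlled ratio was 0.99-1.03 in every scenario, with 1.9-2.7% false falls (nominal 2.5%). The early-switch rule was not simulated there.

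**6. Precision.** At the protocol's rates the means are 0.994 and -ln(1 - 0.16) = 0.174, so 20 women have about 19.9 and 3.5 events, and the log rate ratio is ln(0.174 / 0.994) = -1.74.

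- Before-after: SE = sqrt(1/19.9 + 1/3.5) = 0.58; power = Phi(1.74/0.58 - 1.96), about 85%.
- Randomized months 0-6 (hypothesis 1a): same event counts, so the same SE and power under Poisson counts.
- Controlled change: SE = sqrt(1/19.9 + 3/3.5) = 0.95; power = Phi(1.74/0.954 - 1.96), about 45%.

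**The case against.** The strongest reply is that detection may hardly change. Visits continue every 3 months, the month 9 and 12 visits are paid, culture orders stand, outside results come back, and counts per subject are reviewed quarterly. Women with recurrent, symptomatic infection are likely to seek care without a call. This stands: q may be near 1, and then the bias from lost calls is small. The documents describe no scheduled symptom enquiry at the later visits that would settle it.

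Three stronger readings are tempting, and the documents do not support them.

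- **That entry in a flare makes rates fall.** The entry criterion, "Recurrent UTIs (3 or more in the last year or 2 or more in the last 6 months", inflates the rate before entry. Both periods compared here come after entry, and with stable individual risk they have equal expected rates (step 3). A fall needs fluctuating or declining risk, on which the documents are silent.
- **That false positives reach 14-25%.** Those rates appear only when a 20% natural decline is added to 70% capture. The decline is an assumption.
- **That preventive drugs begun on placebo carry over.** The sentence "Treatment will be up to the discretion of the treating physician" follows the instructions for collecting a specimen in a symptomatic episode and most naturally means treating that episode. Carry-over is possible but not documented.

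It is also fair to say that estrogen starters are not an unchanged control. They may change form at month 6, and after three UTIs their care is left to the provider. If estrogen acts slowly, part of their own decline is drug effect and the contrast is conservative.

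**Conclusion.** The concern holds in a limited form. As planned, hypothesis 1b cannot separate estrogen from period and detection, and the documented imbalance in calls works in favour of the hypothesis. The apparent ratio with no drug effect is 0.95 to 0.75 for assumed capture of 90% to 60%, and 1.00 if capture is complete. The inflation of false positives from lost calls alone is modest at 80-70% capture; it becomes large only with further assumptions about declining or fluctuating risk. The early-switch rule can distort the off-phase rate further.

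A reader might infer that any observed fall would be spurious, or that the efficacy conclusion is compromised. Neither follows. The primary endpoint and hypothesis 1a compare randomized arms over the same months on the same call schedule. This is a point that should be corrected in the analysis plan, not a flaw in the trial's main comparison.

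**What to change.** 1. Report the before-after rate in placebo starters as descriptive, and state that it is not evidence of efficacy. Let hypothesis 1a carry the inference on rates.
2. Alongside it, give the change from months 0-6 to months 6-12 in placebo starters relative to the same change in estrogen starters: the arm-by-period term of a within-woman count model (conditional or random effect) with log observed time as offset, with its confidence interval.
3. Keep the periods by calendar month as randomized. Report how many women switched early and when, and add a sensitivity analysis split at the actual switch date, noting that estrogen starters have no matching switch to cancel its bias.
4. Where preventive drugs are recorded, repeat the analysis with follow-up ended at first use.

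The cost is plan wording and one model term. Enrollment is complete, so the call schedule can no longer readily be equalized, but the counts this analysis needs are already planned in both arms; only dates of preventive drugs may be missing. The price is precision: the controlled contrast has about 45% power at the protocol's assumed effect and rests on some 3.5 events per period among estrogen starters, so a wide interval should be expected and a null result not over-read.
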